13. STATISTICAL CONSIDERATIONS

13.1 Study Design/Endpoints

Cohort A (RAS MUT): Two co-primary objectives are defined for this cohort: proportion of patients alive, progression-free at 6 months following treatment with trametinib and RAI; and objective response rate (ORR, complete response or partial response) at 6 months following treatment with trametinib and RAI. “6 months” (also described below as the “six-month time point”) refers to assessments performed approximately 6 months after the co-administration of RAI with trametinib. (All radiologic assessments performed will be compared back to the baseline scans performed prior to trametinib and RAI therapy.) If either one of these objectives is met, the treatment would be considered worthy of further testing in this disease.

All patients enrolled in the trial who are treated with trametinib through the completion of the second ^{124}I PET scan will be included in determination of these primary endpoints. Patients who are taken off study prior to completion of the second ^{124}I PET scan may be replaced. Patients who are deemed to qualify for treatment with ^{131}I based on the second ^{124}I PET scan, but do not receive it, will be considered to have had a progression/death event and categorized as non-responders. After having received therapeutic ^{131}I , patients who, for any reason, do not have the 6-month evaluation, will be considered to have had a progression/death event and categorized as non-responders. Patients for whom it is determined that the second ^{124}I PET/CT demonstrates insufficient iodine incorporation to warrant treatment with RAI (^{131}I) still have RAI-refractory disease; they will not receive RAI treatment and will be considered to have had a progression/death event and be categorized as non-responders.

It is possible patients will have clinical or RECIST v1.1 radiologic evidence of disease progression prior to the 6-month time point evaluation. These patients may still obtain clinical benefit on the study at the 6-month time point for several reasons: 1) trametinib alone prior to RAI may not have significant clinical efficacy, 2) Thyrogen stimulation can transiently increase tumor size which can be mistaken for disease progression; 3) the therapeutic effects of RAI can be delayed; and 4) evidence of progression may be evident prior to administration of RAI. Hence, patients with evidence of disease progression prior to the 6-month time point evaluation may remain on study at the discretion of the treating physician. The final objective response and disease progression assessments at 6 months for these patients will be based upon a comparison between the 6-month radiologic scan(s) and the baseline, pre-study radiologic scans. The one exception is if a new target or non-target lesion is identified on any radiologic study (including the ^{124}I PET/CT scan) prior to the administration of therapeutic ^{131}I , the first radiologic study prior to ^{131}I that produces a RECIST measurement of the new lesion will be used as the baseline comparator for subsequent evaluations, including assessment of the 6-month response assessment. However, if in the opinion of the treating physician these patients are unlikely to demonstrate benefit at the 6-month time point, the patients will be classified as progression/death event /non-responders and taken off the study.

Patients who receive additional treatment for their thyroid cancer outside of this protocol prior to the 6-month time point (except for thyroid hormone TSH suppression, palliative radiation to a non-target lesion, or therapy to prevent pathologic fractures caused by bone metastases (e.g. zoledronic acid and denosumab)) will be considered to have had a progression/death event and

be categorized as non-responders.

(NOTE: For assessment of ORR, as long as one of the 2 scans required for confirmed PR or confirmed CR designations is performed for the 6 month evaluation, then that patient will be counted as having had a confirmed PR or CR. The other scan required for confirmed PR or CR designation can be obtained on a scan prior to or following the 6 month time point assessment (as long as the two assessments are separated by 4 weeks)).

An exact binomial stage design will be used to discriminate between true 6-month progression/death rates of 20% vs. 50%, and between true ORR rates at 6 months of 5% and 25%. Twenty-five patients will be enrolled. If at least 9 patients are alive, free of progression and have not received additional non-protocol related therapy for thyroid cancer at the 6-month time point, or at least 4 RECIST responses (CR + PR) are observed among the 25 patients at the 6 month time point, this regimen would be considered worthy of further testing in this disease.

This design yields 94% power to detect a true 6-month time point progression/death rate of at least 50%, and 90% power to detect a ORR rate of at least 25%. It yields a 0.05 probability of a positive progression/death result if the true 6-month time point progression/death rate is no more than 20%, and a 0.04 probability of a positive ORR at the 6-month time point result if the true ORR is no more than 5%. Therefore, assuming that progression/death and ORR are independent, the overall type 1 error is <0.1. The type 1 error decreases very slightly if progression/death rate and ORR are positively correlated.

The analysis of progression or death will capture the potential benefit of disease control without continuous treatment that the study strategy provides (as opposed to indefinite, continuous chemotherapy). The pilot study evaluating selumetinib enhancement of RAI therapy had similar eligibility requirements to those in this study, except that the pilot did not require radiographic evidence of disease progression prior to enrollment as this study does. Still, an unplanned, retrospective analysis of 16 patients on the pilot selumetinib study revealed that 15 had evidence of tumor progression on imaging up to one year prior to enrollment, suggesting that the disease for this patient population generally has a propensity to progress. In a phase II study evaluating gefitinib for RAI-refractory thyroid cancer patients (disease progression prior to enrollment was not required) in which some minor reductions in tumor size but no RECIST responses were observed, the median progression-free survival was only 3.9 months (Pennell et al., 2008), corresponding to a 6-month PFS of 34% (under exponential distribution assumption). Because our study requires progression of disease at enrollment, we expect a higher progression rate, therefore assumed a 20% 6-month PFS (null hypothesis). Since all the RAI-refractory patients on the pilot selumetinib study with enhanced RAI incorporation had durable partial responses or stable disease up to 6 months following RAI, we are targeting 50% of patients to be progression-free at the 6 month time point with treatment on this study. For ORR, the assumption that only 5% of these patients would have a RECIST response with RAI alone at the 6-month time point is based upon the premise that we are enrolling a population deemed refractory to RAI alone according to clinical criteria.

Cohort B (BRAF/RAS WT): The primary objective for this arm will be to explore if treatment with trametinib can increase iodine incorporation in thyroid cancer metastases to a predicted lesional absorbed radiation dose equal to or exceeding 2,000 cGy with the administration of \leq

300 mCi RAI. We will consider the treatment worthy of further investigation if at least 3 of the 10 patients enrolled meet this criterion (what we call here “response”). If the true response rate in the population is less than 10%, the probability of seeing 3 or more responses in 10 patients is 7% or less. Therefore, we can be reasonably certain that 3 or more responses are indicative of real drug activity. All patients enrolled in the trial who receive at least one dose of trametinib will be included in determination of these endpoints. Patients who are taken off study prior to receiving one dose of trametinib may be replaced.

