13.5.2 Evaluation of Response

All patients included in the study must be assessed for response to treatment, even if there are major protocol treatment deviations or if they are ineligible. Each patient will be assigned one of the following categories: 1) complete response, 2) partial response, 3) stable disease, 4) progressive disease, 5) early death from malignant disease, 6) early death from toxicity, 7) early death because of other cause, or 9) unknown (not assessable, insufficient data). [Note: By arbitrary convention, category 9 usually designates the “unknown” status of any type of data in a clinical database.]

All of the patients who met the eligibility criteria (with the possible exception of those who received no study medication) and received one dose of trametinib should be included in the main analysis of the response rate. Patients in response categories 4-9 should be considered to have a treatment failure (disease progression). Thus, an incorrect treatment schedule or drug administration does not result in exclusion from the analysis of the response rate. Precise definitions for categories 4-9 will be protocol specific.

All conclusions should be based on all eligible patients. Subanalyses may then be performed on the basis of a subset of patients, excluding those for whom major protocol deviations have been identified (*e.g.*, early death due to other reasons, early discontinuation of treatment, major protocol violations, etc.). However, these subanalyses may not serve as the basis for drawing conclusions concerning treatment efficacy, and the reasons for excluding patients from the analysis should be clearly reported. The 95% confidence intervals should also be provided.

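### Cohort A has two conflicting analysis sets: Section 13.1 uses patients treated through the second PET, with earlier leavers replaceable, while Section 13.5.2 uses all eligible patients with one dose

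*Combined protocol and SAP*

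**What the plan says.** **Section 13.1, Cohort A.** The co-primary endpoints use enrolled patients "who are treated with trametinib through the completion of the second ^{124}I PET scan will be included in determination of these primary endpoints". The next sentence reads "Patients who are taken off study prior to completion of the second ^{124}I PET scan may be replaced", with no limit by reason or by doses taken. Under the Study Calendar (Section 10), trametinib starts on Week 1 Day 6 and the second PET is in Week 5, so a replaceable patient may have had about four weeks of drug. Later in Section 13.1, patients who progress before 6 months and are judged unlikely to benefit are handled differently: "the patients will be classified as progression/death event /non-responders and taken off the study". On size, "Twenty-five patients will be enrolled", and the response cut-off is stated among those 25.

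**Section 13.5.2.** Eligible patients who "received one dose of trametinib should be included in the main analysis of the response rate" form the main set. Categories 4 to 9, which include early death and unknown, count as treatment failure. The section continues: "All conclusions should be based on all eligible patients". Sets that drop patients for reasons such as early discontinuation are allowed as subanalyses, but "these subanalyses may not serve as the basis for drawing conclusions concerning treatment efficacy".

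**Elsewhere.** Section 11.1.1 refers response evaluability to Section 13 as a whole, without ranking its parts. For Cohort B, Section 13.1 uses all enrolled patients with at least one dose and allows replacement only before the first dose.

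**The concern.** Take an eligible Cohort A patient who has been dosed and leaves before the second PET. Section 13.1 lets that patient be replaced. Section 13.5.2 keeps the same patient in the main response analysis as a failure. The set that Section 13.1 makes primary is therefore of the kind that Section 13.5.2 says cannot support an efficacy conclusion.

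The conflict is direct for ORR, because Section 13.5.2 names the response rate. It reaches the progression-free endpoint only through the general sentence on conclusions. Progressors add a further ambiguity: one taken off study before the second PET is a failure under one part of Section 13.1 and replaceable under another.

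At stake are the denominator and confidence interval of the results that decide whether the regimen goes further. They cannot be fixed from the text, so the choice could be made after the results are known. Replacing treated failures would also raise the reported rates.

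**Working it through.** **Inputs (Section 13.1).** n = 25. Null and target rates are 20% and 50% progression-free (printed as progression/death rates, but the rule counts progression-free patients) and 5% and 25% ORR. Success is at least 9 progression-free or at least 4 responses. The documents give no early-leaving rate and replacement is optional, so the number replaced, m, is assumed to be 0 to 3.

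**1. The plan's own figures.** Exact binomial tails at n = 25:
- P(X ≥ 9 | 0.20) = 0.0468 (stated 0.05); P(X ≥ 9 | 0.50) = 0.946 (stated 94%).
- P(X ≥ 4 | 0.05) = 0.0341 (stated 0.04; it rounds to 0.03, a separate matter); P(X ≥ 4 | 0.25) = 0.904 (stated 90%).
- Overall, independent: 1 − (1 − 0.0468)(1 − 0.0341) = 0.079 (stated below 0.1). If every responder is also progression-free (nested; responders given progression-free count K are binomial with size K and probability 0.05/0.20 = 0.25), it is 0.072.

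These figures belong to exactly 25 analysed patients.

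**2. Reported results.** Early leavers are never successes, so only the denominator moves. With m = 2 and exact (Clopper-Pearson) 95% intervals:

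| Successes | Through second PET (13.1) | All eligible dosed (13.5.2) |
|---|---|---|
| 9 | 9/25 = 36.0% (18.0–57.5) | 9/27 = 33.3% (16.5–54.0) |
| 4 | 4/25 = 16.0% (4.5–36.1) | 4/27 = 14.8% (4.2–33.7) |

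**3. Type 1 error if the nulls describe all treated patients and those replaced are failures.** The 25 analysed patients then have null rates 0.20 × (25 + m)/25 and 0.05 × (25 + m)/25.

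| m | Null rates | P(X ≥ 9) | P(X ≥ 4) | Overall, independent / nested |
|---|---|---|---|---|
| 0 | 0.200, 0.050 | 0.0468 | 0.0341 | 0.079 / 0.072 |
| 1 | 0.208, 0.052 | 0.0582 | 0.0386 | 0.095 / 0.085 |
| 2 | 0.216, 0.054 | 0.0715 | 0.0434 | 0.112 / 0.100 |
| 3 | 0.224, 0.056 | 0.0867 | 0.0485 | 0.131 / 0.117 |

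Applying cut-offs 9 and 4 directly to all 25 + m treated patients at 0.20 and 0.05 gives nearly the same: 0.096/0.086 at 26, 0.114/0.102 at 27 and 0.135/0.121 at 28.

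**4. Type 1 error if the nulls describe second-PET completers, or leaving is unrelated to outcome.** The rates among the 25 stay at 0.20 and 0.05, so the overall error stays at 0.079/0.072.

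**5. Which population the rates describe.** Section 13.1 points both ways. The nulls are argued from patients at enrollment: progressive disease on entry for the 20%, and enrolling patients refractory to RAI for the 5%. The 50% target is drawn from pilot patients with enhanced RAI incorporation, who had necessarily completed their second PET.

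**The case against.** The best reply is that Section 13.1 is specific and Section 13.5.2 generic. Section 13.1 names the Cohort A endpoints and says who will be included. Section 13.5.2 sits under a general phase 2 heading, says what should be done, and leaves the precise definitions of categories 4 to 9 to the protocol. Section 13.1 also never says that leavers are excluded, so replacing a leaver while still counting that patient as a failure would satisfy both texts. An evaluable-patient primary set can also be legitimate.

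Part of this stands. Exclusion under Section 13.1 is inferred, from replacement together with a cut-off stated among 25 patients; it is not written. If leavers stayed in, though, the denominator would no longer be 25. The generic-text argument does not settle the matter: Section 13.5.2 is current text and nothing makes it yield. The classification of progressors as failures may also remove the leavers most related to outcome from the replaceable group, but the text does not say whether it overrides replacement.

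A reader might infer that the replacement rule breaks the stated type 1 error bound. The documents do not support that. It needs nulls defined on all treated patients, about two treated patients actually replaced, and those patients being failures. A reader might also infer that the go/no-go decision changes with the denominator. For the same enrolled patients it does not: the written counts of 9 and 4 are met or missed either way.

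**Conclusion.** The two sections conflict and should be reconciled. The contradiction on ORR is plain and does not depend on any leaving rate. For the progression-free endpoint it is indirect. The demonstrable effect is an undetermined denominator and interval, modest in size: 36.0% against 33.3%, and 16.0% against 14.8%, if two treated patients are replaced.

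Any effect on error rates is conditional. Under the all-treated reading with replaced failures, the bound of 0.1 holds with one replacement (0.095/0.085), is reached or passed at two (0.112/0.100) and is passed at three (0.131/0.117). Under the completer reading there is no inflation. This is therefore a point that should be fixed, not one that invalidates the design.

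**What to change.** Reconcile the analysis-set, replacement and progressor text in Section 13.1 with Section 13.5.2, so that Cohort A has one primary set for both endpoints.

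- **Primary set.** Section 13.5.2 already requires all eligible patients with at least one dose. Count those off study before the second PET as progression events and non-responders, and allow replacement only before the first dose, as Cohort B does. Cohort B's rule has no eligibility filter, so state whether dosed but ineligible patients count.
- **Other set.** Keep the through-second-PET set as a labelled subanalysis.
- **Design rates.** State which population the 20%/50% and 5%/25% rates describe.
- **Reporting.** Give the number of treated patients who left before the second PET, with reasons. If any were already replaced, also report rates and exact intervals over all treated patients, and the type 1 error of the 9 and 4 cut-offs at that denominator.

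This changes wording and reporting only and needs no extra patients. The possible cost is power. If the 50% and 25% targets were meant for completers and a fraction d of the 25 leave early, the rates become 0.50(1 − d) and 0.25(1 − d). Power (progression-free/ORR) then falls from 94.6%/90.4% to 91.3%/87.8% at d = 5%, 86.6%/84.7% at 10% and 72.6%/76.6% at 20%. If the targets already describe all treated patients, power is unchanged.

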3.2 Exclusion Criteria

3.2.1 History of another malignancy.

Exception: Patients who have been disease-free for 3 years, patients with a history of completely resected non-melanoma skin cancer, and/or patients with indolent secondary malignancies, are eligible. MSK can consult the CTEP Medical Monitor if unsure whether second malignancies meet the requirements specified above.

3.2.2 History of interstitial lung disease or pneumonitis.

3.2.3 Use of other investigational drugs within 28 days (or five half-lives, whichever is shorter; with a minimum of 14 days from the last dose) preceding the first dose of trametinib and during the study.

3.2.4 Symptomatic or untreated leptomeningeal or brain metastases or spinal cord compression.

3.2.5 Have a known immediate or delayed hypersensitivity reaction or idiosyncrasy to drugs chemically related to trametinib, or excipients or to dimethyl sulfoxide (DMSO) or to thyrotropin alpha (Thyrogen).

3.2.6 Current use of a prohibited medication. The following medications or non-drug therapies are prohibited:

- Other anti-cancer therapy while on study. (Note: Megestrol [Megace] if used as an appetite stimulant is allowed. TSH suppressive therapy is also allowed. Palliative radiation therapy to non-target lesions is also allowed.).
- Concurrent treatment with bisphosphonates is permitted. Prophylactic use of bisphosphonates in patients without bone disease is not permitted, except for the treatment of osteoporosis.
- Because the composition, PK, and metabolism of many herbal supplements are unknown, the concurrent use of all herbal supplements is prohibited during the study (including, but not limited to, St. John's wort, kava, ephedra [ma huang], gingko biloba, dehydroepiandrosterone [DHEA], yohimbe, saw palmetto, or ginseng).

3.2.7 Patients with the following ophthalmological findings/conditions:

- Intraocular pressure >21 mmHg, or uncontrolled glaucoma (irrespective of intraocular pressure)
- Current or past history of central serious retinopathy or retinal vein occlusion

3.2.8 History or evidence of cardiovascular risk including any of the following:

- LVEF $<$ LLN.
- A QT interval corrected for heart rate using the Bazett's formula QTcB ≥ 480 msec.
- History or evidence of current clinically significant uncontrolled arrhythmias (Exception: patients with controlled atrial fibrillation for >30 days prior to randomization are eligible).

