11.1.2 Disease Parameters

Measurable disease. Measurable lesions are defined as those that can be accurately measured in at least one dimension (longest diameter to be recorded) as ≥ 20 mm by chest x-ray or as ≥ 10 mm with CT scan, MRI, or calipers by clinical exam. All tumor

measurements must be recorded in millimeters (or decimal fractions of centimeters).

Note: Tumor lesions that are situated in a previously irradiated area might or might not be considered measurable. *If the investigator thinks it appropriate to include them, the conditions under which such lesions should be considered must be defined in the protocol.*

Malignant lymph nodes. To be considered pathologically enlarged and measurable, a lymph node must be ≥ 15 mm in short axis when assessed by CT scan (CT scan slice thickness recommended to be no greater than 5 mm). At baseline and in follow-up, only the short axis will be measured and followed.

Non-measurable disease. All other lesions (or sites of disease), including small lesions (longest diameter < 10 mm or pathological lymph nodes with ≥ 10 to < 15 mm short axis), are considered non-measurable disease. Bone lesions, leptomeningeal disease, ascites, pleural/pericardial effusions, lymphangitis cutis/pulmonitis, inflammatory breast disease, and abdominal masses (not followed by CT or MRI), are considered as non-measurable.

Note: Cystic lesions that meet the criteria for radiographically defined simple cysts should not be considered as malignant lesions (neither measurable nor non-measurable) since they are, by definition, simple cysts.

‘Cystic lesions’ thought to represent cystic metastases can be considered as measurable lesions, if they meet the definition of measurability described above. However, if non-cystic lesions are present in the same patient, these are preferred for selection as target lesions.

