11.1.4.2 Evaluation of Non-Target Lesions

Complete Response (CR): Disappearance of all non-target lesions and normalization of tumor marker level. All lymph nodes must be non-pathological in size (<10 mm short axis).

Note: If tumor markers are initially above the upper normal limit, they must normalize for a patient to be considered in complete clinical response.

Non-CR/Non-PD: Persistence of one or more non-target lesion(s) and/or maintenance of tumor marker level above the normal limits.

Progressive Disease (PD): Appearance of one or more new lesions and/or *unequivocal progression* of existing non-target lesions. *Unequivocal progression* should not normally trump target lesion status. It must be representative of overall disease status change, not a single lesion increase.

Although a clear progression of “non-target” lesions only is exceptional, the opinion of the treating physician should prevail in such circumstances, and the progression status should be confirmed at a later time by the review panel (or Principal Investigator).

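### Cohort A: non-target progression that is irradiated before 6 months can still be counted as progression-free, because the radiation is exempt whatever its reason and early progression is set aside

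*Combined protocol and SAP*

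**What the plan says.** Four rules bear on this point.

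- **Additional treatment (Section 13.1).** "Patients who receive additional treatment for their thyroid cancer outside of this protocol prior to the 6-month time point" are scored as progression/death events and non-responders, "except for thyroid hormone TSH suppression, palliative radiation to a non-target lesion, or therapy to prevent pathologic fractures caused by bone metastases". The reason for the radiation plays no part. Section 3.2.6 has the matching allowance ("Palliative radiation therapy to non-target lesions is also allowed"), and so does Section 5.1.
- **Early progression (Section 13.1, repeated in the note to 11.1.4.3).** "patients with evidence of disease progression prior to the 6-month time point evaluation may remain on study at the discretion of the treating physician". Their final assessment "will be based upon a comparison between the 6-month radiologic scan(s) and the baseline, pre-study radiologic scans". Four reasons are given: trametinib alone before RAI may be weak, Thyrogen can swell tumours, RAI may act late, and progression may precede RAI. A treating physician who thinks benefit unlikely may classify the patient as an event.
- **What is non-target (Section 11.1.2).** The non-measurable list opens with "Bone lesions, leptomeningeal disease, ascites". Measurable lesions beyond the five targets are also non-target. Non-target lesions need not be measured.
- **When non-target disease is progression (Section 11.1.4.2).** "Appearance of one or more new lesions" qualifies. So does unequivocal worsening of existing non-target lesions, but it must reflect the disease as a whole and not the growth of one lesion.

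Cohort A succeeds on this co-primary if at least 9 of 25 patients are alive and progression-free at 6 months. Section 13.4 applies the same criteria to Cohort B's secondary endpoints.

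**The concern.** The endpoint is meant to show disease control from trametinib-enhanced RAI. Taken separately, each rule can be defended. Together they allow non-target disease to progress by the protocol's own criteria, be irradiated under the exemption, and then be re-read at 6 months as though the progression had not happened. No rule says how an irradiated non-target lesion is to be read at that point.

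None of the four reasons for setting aside early progression covers external beam. It undermines the third, because once a lesion has been irradiated a late RAI effect cannot be told from a radiation effect.

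Such misclassification can only raise the progression-free count. That count is compared with a fixed cut-off, and meeting this co-primary alone is enough to call the regimen worthy of further testing.

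**Working it through.** **1. Is there a path?** A patient is counted wrongly only if all of these hold:

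1. The patient received RAI (patients not given RAI are already events).
2. After baseline, non-target disease met Section 11.1.4.2: worsening that reflects the disease as a whole, or a new lesion. That the exemption reaches a new lesion is a reading; Section 13.1 does speak of new non-target lesions.
3. The lesion was irradiated, and the physician did not classify the patient as an event.
4. At 6 months the irradiated disease is not worse than baseline, target lesions have not progressed, and no other progression is visible.

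Nothing in Section 13.1 or 11.1.4 makes such a patient an event, so the path exists. Each condition narrows it.

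**2. The plan's own figures.** Inputs from Section 13.1: n = 25; success at 9 or more; null 20% and target 50%. These rates are labelled progression/death, but the rationale in 13.1 uses 20% as the 6-month PFS null, and they work only as progression-free rates. The ORR rule is 4 or more of 25, with 5% against 25%.

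Formula: P(X ≥ r) = Σ from k = r to 25 of C(25,k) p^k (1−p)^(25−k).

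- Progression-free, r = 9: 0.0468 at p = 0.20 (stated 0.05); 0.946 at p = 0.50 (stated 94%).
- ORR, r = 4: 0.0341 at p = 0.05 (stated 0.04, slightly high); 0.904 at p = 0.25 (stated 90%).
- Overall error under independence: 1 − (1 − 0.0468)(1 − 0.0341) = 0.079 (stated below 0.1).

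The plan's figures stand, and none allows for misclassification.

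**3. Effect of misclassification.** The documents give no rate of palliative radiation. Let c be the assumed average number of patients in 25 who truly failed but are counted progression-free by this path. The effective null rate is 0.20 + c/25.

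| c (assumed) | Effective null | P(at least 9 of 25) | Overall with ORR rule |
|---|---|---|---|
| 0 | 20% | 0.047 | 0.079 |
| 0.25 | 21% | 0.061 | 0.093 |
| 0.5 | 22% | 0.079 | 0.110 |
| 1 | 24% | 0.123 | 0.153 |

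The overall error reaches 0.1 at an effective null of about 21.4%. That is 1.4 points above 20%, or 0.014 × 25 = 0.35 patients on average.

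**4. Cost of the opposite rule.** Suppose all exempt radiation counted as an event and a share s of truly progression-free patients received it. Power at a true 50% becomes P(X ≥ 9) at p = 0.50(1 − s): 0.946 at s = 0, 0.913 at s = 5% and 0.866 at s = 10%. The values of s are assumptions.

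**The case against.** A reader might infer that any growing lesion controlled by external beam is scored progression-free, with one painful, enlarging bone metastasis as the example. The documents do not support that. Under Section 11.1.4.2 growth of a single non-target lesion is not normally progression, so that patient would usually be progression-free with or without radiation, and the exemption converts nothing. Where progression does reflect the disease as a whole, irradiating one lesion will often leave other worsening lesions visible at 6 months, and those are still progression. The exemption lifts only the additional-treatment event. It does not switch off RECIST, and it does not cover target lesions. Sections 11.1.2 and 11.1.4.2 themselves treat progression confined to non-target lesions as uncommon.

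The set-aside of early progression is also a separate, pre-specified rule, and the radiation allowance is consistent across Sections 3.2.6, 5.1 and 13.1. This is a gap in attribution, not a contradiction.

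Finally, treating every irradiation for pain or swelling as progression would be wrong in the other direction. Section 7.1.3 reports painful swelling of remnant tissue or metastases in 10–20% of patients soon after RAI, and Sections 7.1.2 and 13.1 describe Thyrogen-related enlargement.

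All of this stands, and it limits the size of the problem. It does not close the path: irradiated multi-lesion non-target progression, or an irradiated new lesion no longer visible at 6 months, remains countable. The physician's power to classify such a patient as an event is discretionary.

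**Conclusion.** The concern holds in a narrow form. Section 13.1 allows non-target progression that met the protocol's own criteria, and was then irradiated, to count towards 9 of 25. The bias runs only towards success. ORR is less exposed, because partial response rests on target lesions, whose irradiation is not exempt.

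The size is unknown because no radiation rate is given. On assumed averages of 0 to 1 net conversions in 25, the type I error of the progression-free rule lies between 0.047 and 0.123, and the stated overall limit of 0.1 is passed at about 0.35 conversions. A reader might go further and infer that the true error is 0.12 or more. That would require at least one net conversion in every 25 patients on average, which the documents do not support. Irradiated patients are not the same as converted failures.

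**What to change.** Change the scoring and leave care as it is; palliative radiation stays permitted.

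1. In Section 13.1, state that the set-aside of early progression does not apply to a lesion irradiated after it contributed to RECIST v1.1 progression under Section 11.1.4. That progression stands for the 6-month endpoint. Say how this fits with the existing exception that resets the baseline for a new lesion first seen before RAI.
2. State that radiation for pain or swelling without RECIST progression is not an event in the primary analysis.
3. Record the lesion, date and reason for radiation on the CRF, and report how many patients counted as progression-free were irradiated.
4. Pre-specify a sensitivity repeat of the 9-of-25 rule with all irradiated patients counted as events.

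The cost is a short addition to Section 13.1, a small CRF entry and one extra count. The reported progression-free proportion may be slightly lower. The sensitivity count has less power, as shown in the working, so it should qualify the primary conclusion and not replace it.
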